### 1. Abstract

This is a prospective double-blind, randomized, placebo-controlled trial aims to investigate whether add-on of a standardized extract of cultured Lentinula edodes mycelia (AHCC®) can enhance the effect of immunotherapy in cancer patients.

AHCC is a newly developed functional food. In vitro studies have demonstrated that AHCC enhances natural killer cell activity and may serve as a potent biological response modifier for cancer treatment. Previous research involving 269 HCC patients found that 113 patients who took AHCC orally after curative surgery (AHCC group) experienced significantly longer recurrence-free survival (hazard ratio [HR], 0.639; 95% confidence interval [CI], 0.429-0.952; P = 0.0277) and overall survival (HR, 0.421; 95% CI, 0.253-0.701; P = 0.0009) compared to the control group.

This trial will adopt a two-arm Bayesian optimal phase 2 (BOP2) design (Zhao, 2020). The study will simultaneously evaluate efficacy and toxicity. The null hypothesis assumes a true response rate of 0.27 and a grade 3/4 toxicity rate of 0.57, while the alternative hypothesis assumes a true response rate of 0.42 and a grade 3/4 toxicity rate of 0.36. The trial will be conducted in two stages. In the first stage, 36 patients will be recruited and randomized using block randomization with a block size of 4. The study will be terminated early if fewer patients respond in the AHCC group than in the control group or if 2 or more patients in the AHCC group experience grade 3/4 acute toxicity compared to the control group. Otherwise, the second stage will proceed with the recruitment of an additional 58 patients, bringing the total sample size to 94. If, among the 47 patients in the AHCC group, at least 2 more patients respond compared to the control group or if 2 or fewer patients experience grade 3/4 toxicity, we will reject the null hypothesis and conclude that the treatment is promising. This design controls the type I error rate at 0.1 and achieves a power of 0.75. Considering a 5% dropout rate, each group will enroll 49 patients, resulting in a total sample size of 98.

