Following the Screening period to confirm eligibility, 98 study participants, who meet the entry criteria, will be 1:1 randomized to study intervention (3g of AHCC oral per day or matching placebo) and will be stratified by AFP (<400 vs. ≥400). Enrollment is anticipated to be completed within 2 years, with each participant followed for 6 months since treatment. Therefore, the total duration of the study is expected to be approximately 2.5 years from the time of Institutional Review Board approval. All enrolled participants will receive AHCC or placebo 3g per day until disease progression, intolerance or patient or physician decision to discontinue. Tumor tissue and peripheral blood samples will be collected from all participants for biomarker analysis.

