## 7. Treatment and follow-up plan

- 7.1 All enrolled patients will receive AHCC or placebo 3g every day until disease progression, intolerance or patient or physician decision to discontinue.
- 7.2 During treatment the subjects will be followed according to the follow-up plan summarized in the following table:
  - 7.2.1 Hematology and biochemistry levels will be checked within 72 hours before each administration of study drug treatment.
  - 7.2.2 A window of +/- 7 calendar days is allowable for imaging examination for tumor assessment.
  - 7.3 Prohibited treatment during the study drug treatment period includes the following:
    - 7.3.1 Investigational agents for the treatment of cancer;

7.3.2 Systemic steroids > 10 mg within 14 days of dosing (with a few exceptions eg, steroids for adrenal insufficiency, steroids if taken as part of prophylaxis for CT prep).

	Screen	Treatment Cycles (21-day cycles)					End-of-treatment
	Screen						(EOT) evaluation a
		C1 C2		C3	C4	C5	4 weeks after last
Week		C6	C7	C8	C9	C10	treatment
		:	:	:	:	:	treatment
Informed consent	Х						
Inclusion/exclusion criteria	Х						
Demography/ tumour staging	X						
Medical history	X						
Vital signs	X	Х	Х	Х	Х	Х	X
ECG	X						X
Blood test b	Х		Х	Х	Χ	Χ	Х
Urinalysis	Х					Х	X
HBV/HCV serology markers c	Х						Х
Performance status	Х	Х	Х	Х	Χ	Х	X
Chest X-ray	Х						X
Tumor assessment d	Х					Χ	
Treatment		Х	Х	Х	Х	Х	
Pregnancy test e	Х						
lmmunological study f	Х					Х	Х
Thyroid function g	Х						Х
Tolerability/AE reporting		Χ	Χ	Χ	Х	Х	Х
QOL questionnaire	Х			Х		Χ	Х

- a) The EOT assessment will take place at approximately 1 month after last treatment.
- b) Blood tests will include CBC/DC, albumin, total and direct bilirubin, transaminases (AST and ALT), ALP, AC sugar, sodium, blood urea nitrogen (BUN), creatinine, amylase, lipase, Troponin-T(or hs-cTnT), pro-BNP (brain natriuretic peptide), and creatinine kinase (CK) or CK-MB isoform (CK-MB). Other biochemistry tests may be done at the discretion of individual investigators.

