- c) HBV and HCV serology markers, including HBsAg, anti-HBs, anti-HBs, and anti-HCV, will be checked at baseline only. Subjects who test positive for HBsAg are categorized as chronic HBV infection. Subjects who test positive for anti-HCV are categorized as chronic HCV infection. For subjects with chronic HBV infection, HBV DNA levels should be checked at baseline and at EOT evaluation. For subjects with chronic HCV infection, HCV RNA levels should be checked at baseline and at EOT evaluation.
- d) Tumor assessment (according to RECIST 1.1) will be done every 12 weeks. Computed tomography is the preferred imaging modality and should include imaging of chest and abdomen at baseline and follow-up.
- e) For women with childbearing potential.
- f) In brief, 20ml blood and tumor sample will be collected. Please refer to Sec. 10 for detailed description for collection of each type of samples.
- g) Including serum T3, T4 and TSH.
- h) Quality of life is assessed using the EORTC QLQ-C30 and QLQ-HCC18 at baseline, every 6 weeks and EOT.

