## 8. Assessment of treatment efficacy and safety

- 8.1 Assessment of treatment efficacy
  - 8.1.1 All enrolled patients will receive assessment of tumor response by imaging studies every 12 weeks, according to RECIST version 1.1. Computed tomography is the preferred imaging modality and should include imaging of chest and abdomen at baseline and follow-up.
  - 8.1.2 For subjects who are considered suitable for surgical resection, the actual surgical procedure will be determined by individual treating surgeons and will be recorded. The time frame for holding the study drug prior to surgery will be determined by the treating physician. Participants may resume the study drug after recovery from surgery, at the physician's discretion.
- 8.2 Management of immune-related adverse events (irAE) 7,8
  - 8.2.1 The definition of the most irAE and according management recommendation are summarized in the following table.
  - 8.2.2 For the definition of hepatitis grading, only ALT (alanine aminotransferase) level is used because it is more specific to liver inflammation.
  - 8.2.3 Definition of study drug-induced liver injury (DILI) was listed below, according to the amendment #8 of the CA209040 protocol:
    - 8.2.3.1 Concurrent ALT  $\geq$  10 x ULN AND total bilirubin  $\geq$  2 x ULN or baseline value (if elevated bilirubin at study entry), AND
    - 8.2.3.2 No other immediately apparent possible causes of ALT elevation and hyperbilirubinemia, including, but not limited to, tumor progression, acute viral hepatitis, cholestasis, pre-existing hepatic disease or the administration of other drug(s), herbal medications and substances known to be hepatotoxic.
    - 8.2.3.3 Management of hepatic events, including dose delay and/or discontinuation as well as intervention with steroid treatment, will follow the recommendation listed below, will not be impacted by the definition of DILI.

Types of irAE	Grade 1	Grade 2	Grade 3	Grade 4

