### 11. Statistical consideration

- 11.1 The primary endpoint is ORR in AHCC arm compared to placebo arm. The secondary endpoints include, incidence and severity of adverse events according to CTCAE version 4, progression-free survival and overall survival.
- 11.2 Exploratory endpoints will include correlation of treatment response (tumor shrinkage, objective response rate, etc.) with immune biomarkers in subjects' samples from tumor tissue and peripheral blood.
- 11.3 We simultaneously monitor efficacy and safety endpoints using the 2-arm Bayesian optimal phase 2 (BOP2) design (Zhao et al., 2020).
- 11.3.1 Specifically, let n denote the interim sample size and N denote the maximum sample size. Let E and C denote the experimental arm and the control arm, respectively. For arm t, t = E, C, let  $Y_{eff,t}$  and  $Y_{tox,t}$  respectively denote the efficacy and toxic endpoints, with  $Y_{eff,t} = 1$  and  $Y_{tox,t} = 1$  respectively indicating that patients experience efficacy and toxicity. We assume that the joint distribution of  $\left(Y_{eff,t}, Y_{tox,t}\right)$  follows a multinomial distribution with four elementary

the joint distribution of  $(1_{eff,t},1_{tox,t})$  follows a martinormal distribution with four elementary

outcomes:  $\left(Y_{eff,t},Y_{tox,t}\right)$  = (1, 1), (1, 0), (0, 1) and (0, 0). Let  $\mathbf{p_t} = \left(P_{11,t},P_{10,t},P_{01,t},P_{00,t}\right)$ 

denote the probabilities of observing the four outcomes, and let  $p_{eff,t} = Pr(Y_{eff,t} = 1)$ ,

$$p_{tox,t} = Pr(Y_{tox,t} = 1)$$
 and  $p_{efftox,t} = Pr(Y_{eff,t} = 1, Y_{tox,t} = 1)$ .

11.3.2 The experimental arm is deemed as unacceptable if  $H_0$ :  $p_{eff,E} \leq p_{eff,C}$  or  $p_{tox,E} > p_{tox,C}$ , i.e., the experimental treatment is inefficacious or overly toxic, with respect to the control. We employ the following Bayesian rule to make a go/no-go decision: (Futility and toxicity stopping) stop enrolling patients and claim that the experimental arm is unacceptable if

$$Pr(p_{eff,E} > p_{eff,C}|data) < \lambda \left(\frac{n}{N}\right)^{\alpha}$$
,

[figure not shown]
OR

$$Pr(p_{tox,E} \leq p_{tox,C}|data) < \lambda \left(\frac{n}{N}\right)^{\alpha}$$
,

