where  $\lambda$ =0.68 and  $\alpha$ =0.84 are design parameters optimized to maximize the probability of correctly concluding an efficacious and safe treatment as acceptable when  $p_{eff,E}=0.42$ ,  $p_{tox,E}=0.36$  and  $p_{efftox,E}=0.15$ , while controlling that the probability of incorrectly claiming an inefficacious and toxic treatment, with  $p_{eff,C}=p_{eff,E}=0.27$ ,  $p_{2,C}=p_{2,E}=0.57$  and  $p_{3,C}=p_{3,E}=0.15$ , as acceptable is 10 %. This optimization is performed assuming a vague Dirichlet prior Dir(0.25,0.25,0.25,0.25) for  ${\bf p}$ . The prior is chosen such that it corresponds to a prior effective sample size of 1. The above decision rule leads to the optimal stopping boundaries shown in following tables. The trial stops when either the efficacy endpoint or the toxicity endpoint crosses the stopping boundaries.

[figure not shown]
Optimized stopping boundaries for efficacy endpoint

Interim (no. in control)	Interim (no. in experimental)	No. response (eff) in control	Stop for futility if no. of response in experimental - no. of response in control <=
18	18	0	Never
18	18	1~2	-1
18	18	3~16	-2
18	18	17~18	-1
47	47	0~2	0
47	47	3~12	1
47	47	13~32	2
47	47	33~44	1
47	47	45~47	0

Optimized stopping boundaries for toxicity endpoint

			Stop for unsafety if no. of toxicity in
Interim (no.	Interim (no. in	No. toxicity (tox)	experimental - no. of toxicity in
in control)	experimental)	in control	control >=
18	18	0~1	1
18	18	2~15	2
18	18	16~17	1
18	18	18	Never
47	47	0~3	0
47	47	4~14	-1
47	47	15~34	-2
47	47	35~45	-1
47	47	46~47	0

Based on the above tables and figures, we perform the interim analysis when the number of enrolled patients reaches 36. When the total number of patients reaches the maximum sample size of 94, we reject the null hypothesis and conclude that the experimental arm is acceptable, compared to the control, if both the futility and toxicity stopping boundary are not crossed. Below are the operating characteristics of the design based on 10000 simulations using the BOP2 web application, which is available at http://www.trialdesign.org. Operating characteristics

			Pr(Eff						
			&				Early		
	Pr(Eff	Pr(To	Tox)		Pr(Tox)	Pr(Eff &	Futilit		Avera
	) for	x) for	for	Pr(Eff) for	for	Tox) for	У	Claim	ge
Scena	Contr	Contr	Contr	Experime	Experime	Experime	Stoppi	Promisi	Sampl
rio	ol	ol	ol	ntal	ntal	ntal	ng (%)	ng (%)	e Size
1	0.27	0.57	0.15	0.37	0.47	0.17	23.58	44.40	80.3

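### The interim look is triggered by 36 patients enrolled, not 36 assessed: at the planned accrual about 11 of them would have no tumour assessment

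*Protocol*

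**What the plan says.** Section 11.3.2 sets the timing of the single interim look: "we perform the interim analysis when the number of enrolled patients reaches 36". The boundary tables there have a row set for 18 control and 18 experimental patients. They are entered with the number of responses, or of toxicities, in the control arm, and crossing either boundary stops the trial.

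The efficacy outcome is tumour response. Section 11.1 states: "The primary endpoint is ORR in AHCC arm compared to placebo arm". Note d to the schedule in Section 7 reads "Tumor assessment (according to RECIST 1.1) will be done every 12 weeks", and Section 8.1.1 repeats it: "assessment of tumor response by imaging studies every 12 weeks, according to RECIST version 1.1". Section 7.2.2 adds: "A window of +/- 7 calendar days is allowable for imaging examination for tumor assessment". The first post-baseline response result is therefore due at 11 to 13 weeks.

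The Abstract describes two stages and, after the stage 1 stopping rule, says: "Otherwise, the second stage will proceed with the recruitment of an additional 58 patients". On accrual it states "98 study participants, who meet the entry criteria, will be 1:1 randomized to study intervention" and "Enrollment is anticipated to be completed within 2 years, with each participant followed for 6 months since treatment". No section sets a minimum follow-up or data cut for the 36, and none says that recruitment is suspended.

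**The concern.** The 18-per-arm boundaries assume that response and toxicity are known for all 36 patients. A trigger defined by enrolment fires on the day the 36th patient enters. Everyone enrolled in the preceding 12 weeks then has no scheduled scan, and their toxicity follow-up is only partial. The protocol does not say how such patients enter the comparison.

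At stake is a binding stop/continue decision. With some responses missing, the observed difference between arms can fall on the other side of the boundary in either direction. With some toxicities not yet seen, a check meant to stop a harmful arm becomes less likely to do so. The operating characteristics in Section 11.3.2 would describe a different interim from the one carried out.

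**Working it through.** **Inputs from the protocol.** 98 patients randomised 1:1, enrolment within 24 months, first scan at week 12 (± 1 week), interim at 36 enrolled and final look at 94. Null: response 0.27, toxicity 0.57, joint 0.15 in both arms. Target for AHCC: response 0.42, toxicity 0.36, joint 0.15. Design parameters: λ = 0.68, α = 0.84.

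**Assumptions not in the protocol.** Uniform accrual; unscanned patients counted as non-responders; toxicity onset uniform over the first 12 weeks; 18 and 30 months as alternative enrolment periods.

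**1. Reproducing the protocol's own figures.** The design was simulated with the boundary tables of Section 11.3.2, counting every patient's outcome at each look (1,000,000 trials):

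| Quantity | Protocol | Simulated, all 36 outcomes known |
|---|---|---|
| Scenario 1, early stop | 23.58% | 23.58% |
| Scenario 1, claim promising | 44.40% | 43.7% |
| Scenario 1, average sample size | 80.3 | 80.3 |
| Power at the target | 0.75 | 0.753 |
| Type I error at the null | controlled at 0.1 | 0.090 |

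The protocol's figures are thus obtained when all 36 patients have complete outcomes at the interim.

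**2. Patients without a scan at the trigger.** Rate = 98 / 104.36 weeks = 0.939 per week. Unscanned = 0.939 × 12 = 11.3, which is 31% of 36. That leaves (36 − 11.3) / 2 ≈ 12 assessed per arm. With the imaging window (11 to 13 weeks) the figure is 10.3 to 12.2. It is 9.0 if enrolment takes 30 months and 15.0 if it takes 18.

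**3. Effect on the interim and on the trial.** Simulation of 200,000 trials with randomisation in blocks of 4, comparing the decision at the trigger with the decision on complete data from the same 36 patients:

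| At 24-month accrual | Null | Target |
|---|---|---|
| Stop probability, complete data → as written | 0.51 → 0.48 | 0.10 → 0.12 |
| Missed stops | 11% | 4% |
| False stops | 9% | 6% |
| Interim decisions changed | about 20% | about 9% |
| Claim promising, complete data → as written | 0.09 → about 0.085 | 0.75 → 0.73 |

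Over 30 to 18 months of accrual the share of changed decisions runs from 18% to 24% at the null and from 8% to 11% at the target. Power is 0.72 at 18 months. If toxicity were fully observed and only responses were missing, 11% of decisions would change at the null and 6% at the target, with power 0.74.

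**4. Sensitivity to harm.** For an illustrative AHCC toxicity of 0.75 against 0.57, the probability that the toxicity boundary stops the trial falls from 0.74 to 0.67. It falls to 0.62 if patients with under 12 weeks of follow-up contribute no toxicity.

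**5. Would boundaries recalculated for fewer patients help?** The cutoff is λ(n/N)^α. At n = 36 it is 0.68 × (36/94)^0.84 = 0.304, which reproduces the 18-per-arm rows. At n = 24 it is 0.68 × (24/94)^0.84 = 0.216. For 12 per arm this gives limits of −2 (control responses 2 to 11) and +2 (control toxicities 1 to 10), so the thresholds hardly move. The loss comes from the missing outcomes.

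**The case against.** The strongest reply is that the trigger is being read too literally. The Abstract makes stage 2 recruitment depend on comparing responses among the first 36, so stage 1 must be evaluated first, and 36 enrolled may simply name the size of the look. The final look is worded in the same way (when the total reaches 94), and nobody reads that as an analysis on the day the last patient enters. Data cut-offs are also often left to an analysis plan or a monitoring charter.

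Part of this stands: a hold may well be intended. But suspending recruitment is not a data cut. An analysis run when the 36th patient enters lacks the same scans whether or not recruitment then stops. The final look differs because the timeline provides for it: 24 months of enrolment plus 6 months of follow-up make up the 2.5-year study, with no separate allowance for a 12-week wait at the interim. Nor is the point silently deferred to a later document, because the protocol fixes the trigger itself, and on enrolment.

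The second reply is that the effect looks larger than it is. This is largely fair. Under the null the complete-data stop is close to a coin toss, so many changed interim decisions have no consequence: only about 1.5% of null trials and 5.5% of target trials end with a different final verdict. In the illustrative high-toxicity case, taking AHCC response as 0.27 and the joint probability as 0.20, overall early stopping falls from 0.81 to 0.76 and a promising claim stays near 0.3%. Adverse events are reviewed every 3 weeks, so toxicity may be more complete than assumed here. These points limit the size of the problem but do not remove it.

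**Conclusion.** The concern holds. Followed as written, the interim applies boundaries built for 36 complete outcomes when about 11 patients (31%) have no response assessment. That count uses the protocol's own 98 patients, 24 months and 12-week scan plus uniform accrual. Because 24 months is an upper limit on enrolment, 11 leans low; early progression or death would reduce the number without a status.

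The harm is to the interim decision: about one in five decisions changes under the null and about one in eleven under the target, and the toxicity stop loses sensitivity. These rates depend on the assumed handling of unscanned patients and on the assumed toxicity onset. Power falls by 1 to 2 points at the planned accrual, type I error does not rise, and the final analysis is unaffected. This should be corrected, but it does not undermine the trial's main conclusion.

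**What to change.** Replace the trigger in Section 11.3.2 with wording such as: *The interim analysis is performed when the first 36 randomised patients have completed the first scheduled (week-12) tumour assessment, with toxicity recorded up to that visit, or have progressed, died or withdrawn earlier. The 18-per-arm boundaries are applied to these 36 patients only.* State in both the Abstract and Section 11.3.2 whether enrolment is held until the decision, so that the two agree.

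The cost is two or three sentences. Boundaries and sample size stay the same, and the simulated operating characteristics then apply. The interim moves about 12 weeks later: 36 / (98/24) = 8.8 months, plus 2.8 months, gives about month 11.6. If accrual continues meanwhile, about 11 more patients (9 to 15) enrol before the decision. If it is held, enrolment lengthens by about 12 weeks and the stated timeline should reflect that.

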- 8.6.5 An Adverse Event (AE) is defined as any new untoward medical occurrence or worsening of a preexisting medical condition in a clinical investigation participant administered study drug and that does not necessarily have a causal relationship with this treatment. An AE can therefore be any unfavorable and unintended sign (such as an abnormal laboratory finding), symptom, or disease temporally associated with the use of investigational product, whether or not considered related to the investigational product.
- 8.6.6 The causal relationship to study drug is determined by a physician and should be used to assess all adverse events (AE). The casual relationship can be one of the following:
  - 8.6.6.1 Related: There is a reasonable causal relationship between study drug administration and the AE.
  - 8.6.6.2 Not related: There is not a reasonable causal relationship between study drug administration and the AE.
  - 8.6.6.3 The term "reasonable causal relationship" means there is evidence to suggest a causal relationship.
  - 8.6.6.4 Adverse events can be spontaneously reported or elicited during open-ended questioning, examination, or evaluation of a subject. (In order to prevent reporting bias, subjects should not be questioned regarding the specific occurrence of one or more AEs.)
  - 8.6.6.5 Nonserious AE information should also be collected from the start of a placebo lead-in period or other observational period intended to establish a baseline status for the subjects.
  - 8.6.6.6 The collection of nonserious AE information should begin at initiation of study drug. All nonserious adverse events (not only those deemed to be treatment-related) should be collected continuously during the treatment period and for a minimum of 30 days following the last dose of study treatment.
  - 8.6.6.7 Nonserious AEs should be followed to resolution or stabilization, or reported as SAEs if they become serious. Follow-up is also required for nonserious AEs that cause interruption or discontinuation of study drug and for those present at the end of study treatment as appropriate.
- 8.6.7 All laboratory test results captured as part of the study should be recorded following institutional procedures. Test results that constitute SAEs should be documented and reported as such. The following laboratory abnormalities should be documented and reported appropriately:
  - 8.6.7.1 any laboratory test result that is clinically significant or meets the definition of an SAE

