- 11.4 The primary endpoint analysis and other secondary endpoints will be based on the intent-to-treat population and per-protocol population, while the safety data will be summarized based on the intent-to-treat population.
  - 11.4.1 Intent-to-treat population refers to all enrolled patients regardless of their compliance with the study drug treatment.
- 11.4.2 Per-protocol population refers to all patients who have received at least 6 weeks (2 cycles) of study medication and received the first scheduled assessment of tumor response.
  - 11.5 Disease stabilization rate (complete response + partial response by RECIST + stable disease by RECIST that last for  $\geq 8$  weeks), objective response rate (complete response + partial

- response by RECIST), and down-staging rate will be calculated with their 95% confidence intervals.
- 11.6 Progression-free survival, time-to-tumor progression, and overall survival will be calculated by the Kaplan-Meier method.
- 11.6.1 Progression-free survival is defined as the duration from the date of the first dose of study drug treatment to the date of documented disease progression or death of any cause.
- 11.6.2 Time-to-tumor progression is defined as the duration from the date of the first dose of study drug treatment to the date of documented tumor progression by imaging studies.
- 11.6.3 Overall survival is defined as the duration from the date of the first dose of study drug treatment to the date of death of any cause.
  - 11.7 The baseline and changes in immune-related biomarkers after study drug treatment will be correlated with the patients' treatment outcome, including disease stabilization, best radiographic response, time to tumor progression, progression-free survival, and overall survival.
  - 11.8 For the endpoint of the safety assessment, the tabulations will count the number of subjects reporting individual adverse events. Incidence of adverse events and serious adverse events will be summarized.
  - 11.9 The demographic features of the subjects will be summarized by descriptive statistics. Comparison between sub-groups, for examples, subjects with vs. without objective tumor response/AFP response/disease stabilization subjects with vs. without surgery after study drug treatment by using Mann-Whitney tests/ one-way ANOVA (continuous variables) or chisquare/Fisher's Exact tests (categorical variables).

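### PFS, TTP and OS are counted from first dose, so a randomised patient who never starts cannot enter the intent-to-treat analysis the protocol specifies; safety has the reverse, smaller mismatch

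*Protocol*

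**What the plan says.** **Analysis sets.** Section 11.4 states: "The primary endpoint analysis and other secondary endpoints will be based on the intent-to-treat population and per-protocol population". Section 11.4.1 gives the definition: "Intent-to-treat population refers to all enrolled patients regardless of their compliance with the study drug treatment". It sets no dosing condition. The per-protocol set in 11.4.2 requires at least two cycles of study medication and the first scheduled tumour assessment.

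**Time origins.** Sections 11.6.1 to 11.6.3 use one origin for all three endpoints:
- PFS: "Progression-free survival is defined as the duration from the date of the first dose of study drug treatment".
- TTP: "Time-to-tumor progression is defined as the duration from the date of the first dose of study drug treatment".
- OS: "Overall survival is defined as the duration from the date of the first dose of study drug treatment".

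**Safety.** Under 11.4, "the safety data will be summarized based on the intent-to-treat population". Section 11.8 counts subjects who report events. Section 8.6.5 defines an adverse event as occurring in a participant who has been given study drug, and 8.6.6.6 says: "The collection of nonserious AE information should begin at initiation of study drug". No dosed-only safety set is defined, and no rule covers an enrolled patient who never starts.

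**The concern.** Intent-to-treat analysis compares everyone as randomised. A clock that starts at first dose needs an event, taking the drug, that comes after randomisation and need not happen. For a patient without that event the analyst must either drop the patient, which is no longer intent-to-treat, or supply an origin the protocol does not state. A death between randomisation and first dose has no place in the definition of OS, and the same holds for an early progression in PFS and TTP. If this is settled after data are seen, the choice can follow the results.

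For safety the set is too wide rather than the clock too late. Undosed patients sit in the denominator, while the AE definition and the nonserious collection rule leave them little or nothing to contribute to the numerator. Reported rates are then diluted.

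**Working it through.** **1. The survival definitions set against the analysis sets.**

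| Set | Everyone has a first dose? | First-dose origin workable? |
|---|---|---|
| Per-protocol (11.4.2) | Yes, at least two cycles taken | Yes |
| Intent-to-treat (11.4.1) | Not required | No, for anyone undosed |

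The 11.6 definitions fit the per-protocol set but not the intent-to-treat set that 11.4 also names. No arithmetic is needed for this half.

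**2. The design's own figures, reproduced.** The printed boundaries in 11.3 (18 and 47 per arm) were simulated with 400,000 runs and multinomial response and toxicity outcomes.

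| Scenario | Protocol | Recomputed |
|---|---|---|
| Scenario 1: early stop / promising / average N | 23.58% / 44.40% / 80.3 | 23.6% / 43.6% / 80.3 |
| Alternative (0.42 response, 0.36 toxicity): promising | 0.75 | 75.2% |
| Null (0.27 response, 0.57 toxicity): promising | limit 0.10 | 8.9% |

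The agreement is close enough to use the model for sensitivity.

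**3. Dilution of the toxicity rate.** Inputs: the null grade 3/4 toxicity rate of 0.57 (abstract), 47 per arm (11.3), and k undosed patients in the arm. The protocol does not give k, so 1, 2 and 5 are assumed. With no toxicity recorded for undosed patients, the reported rate is 0.57 × (47 − k)/47:
- k = 1: 0.57 × 46/47 = 0.558
- k = 2: 0.57 × 45/47 = 0.546
- k = 5: 0.57 × 42/47 = 0.509

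**4. Effect on the go/no-go rule.** Here k second-stage patients are scored as toxicity-free, which is again an assumption.

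| Undosed patients | False-promising rate under the null |
|---|---|
| None | 8.9% |
| Equal in both arms, k = 1 to 5, response unchanged | 8.8% to 9.0% |
| AHCC arm only, response unchanged | 10.0% (k = 1), 11.3% (k = 2), 14.6% (k = 5) |
| AHCC arm only, counted as non-responders | 9.5% (k = 1), about 10% (k = 2), 10.5% (k = 5) |

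With balanced non-dosing and response unchanged, power moves from 75.2% to 74.1% at k = 5.

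**The case against.** **On survival.** PFS and OS are secondary and stand outside the go/no-go rule, and 11.6 specifies only Kaplan-Meier estimation. With imaging every 12 weeks, few progressions could be documented between randomisation and first dose, so the uncounted events would mainly be early deaths. This limits the size of the problem. It does not remove the conflict between 11.4.1 and 11.6.

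**On safety.** It would be too strong to say that adverse events are collected only from first dose. Section 8.6.6.6 covers nonserious events. Section 8.3 has patients followed every three weeks for adverse events without mentioning dosing, 8.5.7 counts second malignancy from consent, and 8.6.6.5 mentions a lead-in or observational period, although the design describes none. That undosed patients would count as largely event-free is an inference from 8.6.5, 8.6.6.6, 11.4 and 11.8 read together; no sentence says so. This objection stands, which is why safety is the secondary point.

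**On size.** A reader might take the 5% dropout figure, 98 × 0.05 = 4.9 patients, as the number undosed. The protocol gives 5% as general dropout and states no never-dosed rate. The 49 per arm also includes that allowance on top of the 47 to which the boundaries apply.

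**Conclusion.** The point holds. The stated time origin defeats the stated intent-to-treat analysis of PFS, TTP and OS for any randomised patient who never starts study drug. That follows from the protocol's text and rests on no assumption about numbers. The safety mismatch is real but inferred, and lesser.

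The numerical effect is probably small. It depends on a count of undosed patients that the protocol does not give. For 1, 2 or 5 of 47, a 0.57 toxicity rate would read about 0.56, 0.55 or 0.51.

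A reader might go further. With 15 to 34 control toxicities, the final boundary requires at least three fewer in the AHCC arm, so one or two undosed patients might seem able to swing the decision. The documents do not support that. The trial is double-blind, and a patient who never starts cannot be reacting to the product, so balanced non-dosing is the expected case, and there the false-promising rate stays near 9%. Even if all undosed patients were in the AHCC arm, the result depends on how their response is scored: one or two give 9.5% to about 10% as non-responders, and about 10% to 11.3% if response is left unchanged.

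**What to change.** - In 11.6.1 to 11.6.3, define PFS, TTP and OS from the date of randomisation, for all randomised patients.
- Record the randomisation date if it is not already captured. The registration data listed in section 6.2 do not name it, so its availability should be checked.
- In 11.4, summarise safety in patients who took at least one dose of AHCC or placebo.

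The cost is a wording change and possibly one extra date field. The sample size and the printed boundaries are not affected. The change is best made before unblinding, so that neither the origin nor the exclusions can be chosen with results in view.
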